8.3. Multivariate analyses

If appropriate, exploratory Cox regression for multivariate analysis of main covariate effects will be used for time-dependent efficacy parameters, and logistic regression for the evaluation of covariates associated with best overall response.

8.4. Fixed, random or mixed effects models

Not applicable.

8.5. Subgroup Analysis

Not applicable.

8.6. Interim Analysis

A futility analysis is planned when 12 patients evaluable for efficacy are recruited according to the Simon's design. Other non-scheduled analyses might be performed exclusively for enhancing patient's safety.

8.7. Independent review committee

Because of safety reasons, an independent cardiologist will undertake a review of all the ECGs and echocardiograms performed to the patients during the course of the study, in order to evaluate the cardiotoxicity risk of PM00104. For this purpose, an independent cardiologist's report not included in this SAP will be presented as an Appendix of the CSR.

9. Statistical software

Oracle Clinical will be used for double data entry and clinical data management.

SAS v9.2 will be used for all the statistical analysis.

TABLES, LISTINGS AND FIGURE SHELLS

NOTE: Each particular table, listing and figure will have a comprehensive header and/or footnotes. If the number of items would not yield appropriate tabular or graphic representations, detailed listings will be shown instead.

TABLE 10.1.1.1 PATIENTS DISPOSITION BY INSTITUTION.	17
TABLE 10.1.1.2 LISTING OF PATIENTS NOT ELIGIBLE.	17
TABLE 10.1.1.3 LISTING OF PATIENTS INCLUDED BUT NOT TREATED.	17
TABLE 10.1.1.4 LISTING OF PATIENTS NOT EVALUABLE FOR SAFETY.	17
TABLE 10.1.1.5 LISTING OF PATIENTS NOT EVALUABLE FOR EFFICACY.	17
TABLE 10.1.2.1 STUDY DATES.	17
TABLE 10.1.3.1 REASONS FOR TREATMENT DISCONTINUATION.	18
TABLE 10.1.3.2 REASONS FOR TREATMENT DISCONTINUATION BY NUMBER OF CYCLES RECEIVED	18
TABLE 10.1.3.3 TIME ON TREATMENT (MONTHS)	
TABLE 10.1.3.4 LISTINGS OF PATIENTS AND TIME ON TREATMENT.	
TABLE 10.1.3.5 LISTINGS OF TREATMENT DISCONTINUATION OTHER THAN PROGRESSIVE DISEASE	
TABLE 10.1.3.6 LISTING OF TREATMENT DISCONTINUATION DUE TO ADVERSE EVENTS (AES)	18
TABLE 10.1.3.7 LISTING OF TREATMENT DISCONTINUATION DUE TO DEATH.	
TABLE 10.1.4.1 REASON FOR STUDY DISCONTINUATION.	
TABLE 10.1.4.2 LISTING OF OTHER REASONS STUDY DISCONTINUATION.	
TABLE 10.1.5.1 ELIGIBILITY: PATIENTS WHO ENTERED THE STUDY EVEN THOUGH THEY DID NOT	
SATISFY THE ENTRY CRITERIA.	19
TABLE 11.1.1.1 BASELINE CHARACTERISTICS: SUMMARY STATISTICS.	
TABLE 11.1.1.2 SUMMARY STATISTICS: BASELINE CHARACTERISTICS.	
TABLE 11.1.2.1 TUMOR HISTOLOGY.	
TABLE 11.1.2.2 SITES FOR TARGET AND NON-TARGET LESIONS.	
TABLE 11.1.2.3 LISTING OF PATIENT HISTOLOGY.	
TABLE 11.1.2.4 LISTING OF TARGET AND NON TARGET LESIONS.	
TABLE 11.1.2.5 SUMMARY STATISTICS OF CANCER DIAGNOSIS CHARACTERISTICS: TIME FROM	1
DIAGNOSIS AND TIME FROM LAST PROGRESSION DISEASE (PD) TO FIRST INFUSION OF STUDY DRUG	21
TABLE 11.1.3.1 SURGERY (PALLIATIVE + CURATIVE).	
TABLE 11.1.3.2 RADIOTHERAPY.	
TABLE 11.1.3.3 PATIENTS WITH PRIOR SURGERY.	

10.1. General characteristics

10.1.1. Patients disposition

Table 10.1.1.1 Patients disposition by institution.

	Instit	ution 1	Insti	tution 2		••••	T	otal
	N	%	N	%	N	%	N	%
N-eligible								
N-included								
N-treated								
N-evaluable for safety								
N-evaluable for efficacy								

NOTE: See listings from 10.1.1.2 to 10.1.1.5

Table 10.1.1.2 Listing of patients not eligible.

Patient ID	Reason

Table 10.1.1.3 Listing of patients included but not treated.

Patient ID	Reason
- 	•

Table 10.1.1.4 Listing of patients not evaluable for safety.

Patient ID	Reason

Table 10.1.1.5 Listing of patients not evaluable for efficacy.

Patient ID	Reason

10.1.2. Study dates

Table 10.1.2.1 Study dates.

Event	Date
Date first consent	
Date first dose of first patient	
Date last consent	
Date first dose of last patient	
Date last dose	
Last follow up date	

10.1.3. Reasons for treatment discontinuation

Table 10.1.3.1 Reasons for treatment discontinuation.

	T	Total		
	N	%		
Progressive disease				
Toxicity (Drug related AE)*				
Death**				
Patient refusal				
Investigator decision				
Other***				

(*) See tables 10.1.3.6; (**) Table 10.1.3.7; (***) Table 10.1.3.5

Table 10.1.3.2 Reasons for treatment discontinuation by number of cycles received.

	Cyc	cle 1	Cyc	cle 2		•••	-	Fotal
	N	%	N	%	N	%	N	%
Progressive disease Patient refusal								

Table 10.1.3.3 Time on treatment (months).

|--|

^(*) Time from first infusion of the study drug to the day of the last study drug administration plus 30 days, or onset of subsequent therapy or death, whichever occurs first.

Table 10.1.3.4 Listings of patients and time on treatment.

Patient ID.	Day of first infusion	Day of last dose administered	Number of cycles received	Time on treatment (months)
				· · · · · · · · · · · · · · · · · · ·

Table 10.1.3.5 Listings of treatment discontinuation other than progressive disease.

Patient ID.	Cycle	Reason	Specify

Table 10.1.3.6 Listing of treatment discontinuation due to adverse events (AEs).

Patient ID.	PT MedDRA Code	Grade		Relationship	Significant
1 attent 1D.	1 1 MedDKA Code	Grauc	•••	Relationship	consequence

Table 10.1.3.7 Listing of treatment discontinuation due to death.

Patient ID. Cycle	Cause of death	Last study drug administration date	Death date	Time from last Study drug administration to death (days)
•				

10.1.4. Reasons for patient's study discontinuation

Table 10.1.4.1 Reason for study discontinuation.

Total		
N	%	

(*)See table 10.1.4.2

Table 10.1.4.2 Listing of other reasons study discontinuation.

Patient ID	Reason	Specify

10.1.5. Protocol deviations

Table 10.1.5.1 Eligibility: Patients who entered the study even though they did not satisfy the entry criteria.

Patient ID Deviation type* Deviation description	**
--	----

^(*) Including but not restricted to: Inclusion/Exclusion deviations, study procedures not performed, patients developing withdrawal criteria who were not withdrawn, patients who received incorrect dose or schedule, patients who received an excluded concomitant medication, and patients who do not satisfy criteria for treatment continuation.

^(**) Deviations with no effects on the risk/benefit ratio of the clinical trial will be distinguished from those that might have an effect on this risk/benefit ratio.

11. Appendix II. Demographic analysis and efficacy evaluation

11.1. Baseline characteristics

11.1.1. Patients characteristics at baseline

Table 11.1.1.1 Baseline characteristics: Summary statistics.

		Total (N=XX)		
		N	,	%
Gender				
Male				
Female				
Age grouped:				
16 – XX years				
XX – YY years				
≥ YY years				
Table 11.1.1.2 Summary statistic	es: baseline ch	aracteristics.		
	N	Median	Min	Max
Age (years)	·			
,				
11.1.2. Histology ar	nd time from	diagnosis		
Table 11.1.2.1 Tumor histology.				
			Tot	al (N=XX)
			N	%
Tumor diagnosis:				
Ewing's bone sarcoma				
Extraosseous Ewing:				
PNET				
Askin				
Other*				
Primary tumor site:				
Upper extremity				
Lower extremity				
Face and neck				
Trunk/abdominal wall				
Other**				
Current Disease				
Unresectable locally advanced	disease			
Metastatic	t-non target):	•		
Metastatic Number of sites involved (targe	· · · · · · · · · · · · · · · · · ·			
Number of sites involved (targe	· · · · · · · · · · · · · · · · · · ·			
Number of sites involved (targe 1 2	·· ····· g -·/			
Number of sites involved (targe	······································			

Summary statistics of number of sites involved (target-non target):

Ň

Median

Minimum

Maxim	un

Programming Notes: Percentage is based on total patient included.

(*) and (**) See listing 11.1.2.3

Table 11.1.2.2 Sites for target and non-target lesions.

Sites	7	Total		
Sites	$oldsymbol{N}$	%		
Bone				
Lung				
••••				

Table 11.1.2.3 Listing of patient histology.

Dadiant ID	Tumor	Primary tumor	TNM at	Stage at	Other,	Current
Patient ID.	diagnosis	site	Diagnosis	Diagnosis	Specify	stage

Table 11.1.2.4 Listing of target and non target lesions.

Patient ID.	Target/non-target	Site/Subsite	Method

Table 11.1.2.5 Summary statistics of cancer diagnosis characteristics: Time from diagnosis and time from last progression disease (PD) to first infusion of study drug.

	N	Median	Min	Max
Time from first diagnosis to first infusion				
(months)				
Time from last progression to first infusion				
(months)				

11.1.3. Prior anticancer therapy

Table 11.1.3.1 Surgery (palliative + curative).

	N	%
Yes		
No		
Table 11.1.3.2 Radiotherapy.		
	N	%
Yes		

Table 11.1.3.3 Patients with prior surgery.

No

Patient ID.	Intention	Site and Procedures	Surgery Date	Residual disease

Table 11.1.3.4 Summary statistics of prior systemic anticancer therapy.

	N	Median	Min	Max
Number of lines				
Number of agents				

Table 11.1.3.5 Number of lines and agents of systemic anticancer therapy.

	Total (N=XX)			
	N	%		
Number of lines				
1				
2				
3				
> 3				
Number of agents				
1				
2				
3				
> 3				

Table 11.1.3.6 Summary of lines and agents of systemic anticancer therapy.

Antineoplastic and immunomodulating agents (ATC-clas. Levels 1-4)	N	%
Antineoplastic Agents (L01)		

11.1.4. Prior history

Table 11.1.4.1 Prior history.

Patient ID.	Description	Onset date	Resolved date

11.1.5. Physical examination, vital signs, electrocardiogram and other tests

Table 11.1.5.1 Physical examination at baseline.

		Total (N=XX)		
D		N %		
Physical Examina	tion:			
Normal				
Abnormal				
ECOG-PS:				
0				
2				
2				
ECG:				
Normal				
Abnormal				
LVEF				
Normal				
Abnormal				
	Not applicable" and specify reasons	s will be giving in a supportive lie		
() 1471 Stantas 101	That applicable and specify reasons	will be giving in a supportive its		
T 11 11 1 5 2 1				
	tings of patients with positive pregn	ancy test.		
Patient ID.		ple date		
Table 11.1.5.3 Lis	tings of patients with no adequate co	ontraception.		
	tings of patients with no adequate co			
Table 11.1.5.3 Lis	tings of patients with no adequate co	ontraception.		
Table 11.1.5.3 Lis Patient ID.	tings of patients with no adequate co	ontraception.		
Table 11.1.5.3 Lis Patient ID. Table 11.1.5.4 Lis	tings of patients with no adequate constants. Sam	ontraception. ple date		
Table 11.1.5.3 Lis Patient ID.	tings of patients with no adequate co	ontraception.		
Table 11.1.5.3 Lis Patient ID. Table 11.1.5.4 Lis Patient ID.	tings of patients with no adequate constants. Sam	ontraception. ple date Specify*		
Table 11.1.5.3 Lis Patient ID. Table 11.1.5.4 Lis Patient ID. (*) If available deta	Sam Sting of ECOG performance status. ECOG ails will be extracted from signs and	Specify* symptoms.		
Table 11.1.5.3 Lis Patient ID. Table 11.1.5.4 Lis Patient ID. (*) If available deta	stings of patients with no adequate constants. ECOG	Specify* symptoms.		
Table 11.1.5.3 Lis Patient ID. Table 11.1.5.4 Lis Patient ID. (*) If available deta	Sam Sting of ECOG performance status. ECOG ails will be extracted from signs and	Specify* symptoms.		
Table 11.1.5.3 Lis Patient ID. Table 11.1.5.4 Lis Patient ID. (*) If available deta Table 11.1.5.5 Lis Patient ID.	Sam Sting of ECOG performance status. ECOG Ails will be extracted from signs and ting of patients with abnormal ECG ECG result	Specify* symptoms. at baseline. Specify*		
Table 11.1.5.3 Lis Patient ID. Table 11.1.5.4 Lis Patient ID. (*) If available deta Table 11.1.5.5 Lis Patient ID.	Sam Sting of ECOG performance status. ECOG ails will be extracted from signs and ting of patients with abnormal ECG	Specify* symptoms. at baseline. Specify*		
Table 11.1.5.3 Lis Patient ID. Table 11.1.5.4 Lis Patient ID. (*) If available deta Table 11.1.5.5 Lis Patient ID.	Sam Sting of ECOG performance status. ECOG Ails will be extracted from signs and ting of patients with abnormal ECG ECG result	Specify* symptoms. at baseline. Specify*		
Table 11.1.5.3 Lis Patient ID. Table 11.1.5.4 Lis Patient ID. (*) If available deta Table 11.1.5.5 Lis Patient ID. (*) If available deta	Sam Sting of ECOG performance status. ECOG Ails will be extracted from signs and ting of patients with abnormal ECG ECG result	Specify* symptoms. at baseline. Specify*		

Parameter	N	Median	Min	Max
Weight (Kg)				
Height (cm)				
Heart rate (beats/min)				
BPS (mmHg)				
BPD (mmHg)				
Temperature (°C)				

11.1.6. Hematological values at baseline

Table 11.1.6.1 Hematological abnormalities at baseline.

Parameter*	Gra	Grade 1		Grade 2		Grade 3		Grade 4		Total (G1-G4)	
Parameter.	N	%	N	%	N	%	N	%	N	%	
Anemia											
Lymphopenia											
Neutropenia											
Thrombocytopenia											

(*) All hematological abnormalities susceptible to be graded in NCI-CTCAE v4.0

Table 11.1.6.2 Hematology at baseline. Last value before treatment.

Parameter*	N	Median	Min	Max
Hemoglobin				_
Lymphocytes				
Neutrophils				
Platelets				

(*) Units for Leukocytes, Lymphocytes, Neutrophils and Platelets are in 10^9 /l. Hemoglobin in g/dl

Table 11.1.6.3 Hematology at baseline: Patients with hematological parameters missing.

Patient ID.	Parameter

Table 11.1.6.4 Hematology at baseline. Abnormalities grade ≥ 2 .

Patient ID.	Parameter	Value	Grade

11.1.7. Biochemical values at baseline

Table 11.1.7.1 Biochemical abnormalities at baseline.

Doromotor*	Gra	Grade 1		de 2	Gra	de 3	Gra	de 4	Total	(G1-G4)
Parameter*	N	%	N	%	N	%	N	%	N	%
AST										
ALT										
*										

(*) Total bilirubin, AP, CPK and Creatinine. All biochemical abnormalities susceptible to be graded in NCI-CTCAE v4.0

Table 11.1.7.2 Biochemistry at baseline. Last value before treatment.

Parameter* Median Min N Max AST ALT Total Bilirubin (*) Units for AST, ALT, AP, CPK are IU/l. Units for Total Bilirubin and Creatinine are mg/dl. Table 11.1.7.3 Biochemistry at baseline. Patients with missing biochemical parameters. Patient ID. **Parameter** Table 11.1.7.4 Biochemistry at baseline. Abnormalities grade ≥ 2 . Patient ID. **Parameter** Value Grade 11.1.8. Other metabolic values at baseline Table 11.1.8.1 Other metabolic abnormalities at baseline (hyper-hypo). Grade 2 Grade 3 Total (G1-G4) Grade 1 Grade 4 Parameter* % N N % N % N % N % Hyperglycemia (*) Hyper and hypo abnormalities and all metabolic parameters susceptible to be graded as per NCI-CTCAE v4.0; i.e, Glucose, Sodium, Potassium, Calcium, Magnesium and Albumin. Table 11.1.8.2 Other metabolic abnormalities at baseline. Last value before treatment. Parameter* Median Min Max Glucose (*) Units for Glucose, Sodium, Clorhide, Potassium, Calcium, Magnesium are in mmol/l; Albumin and Total proteins in g/dl and LDH in IU/l; Creatinine Clearance (CrCl) in ml/min. Table 11.1.8.3 Patients with missing metabolic parameters. Patient ID. Parameter Table 11.1.8.4 Other metabolic at baseline. Abnormalities grade ≥ 2 . Patient ID. **Parameter** Value Grade

11.1.9. Signs and symptoms at baseline

Table 11.1.9.1 Summary statistics: Signs and symptoms.

SOC/MedDRA	Grade 1	Grade 2	Grade 3	Grade 4	Total (N=XX)
------------	---------	---------	---------	---------	--------------

Preferred t	term	N	%	N	%	N	%	N	%	N	%
General	Abdomina										
Disorders	Distension										
Pain											

Table 11.1.9.2 Median of signs and symptoms

N	Median	Min	Max

Table 11.1.9.3 Listing of baseline characteristics: Signs and symptoms (Grade ≥ 2).

Patient SOC Sign/symptom Verbatim (PT) term	Grade Onset date Relationship Treated
---	---------------------------------------

11.1.10.Concomitant therapy

Table 11.1.10.1 Agents of concomitant therapy started at baseline.

Concomitant medication (ATC1/ATC2/ATC4)						
System(ATC1)	Indication(ATC2)	Agents(ATC4)	N	%		
Alimentary tract and metabolism	Stomatological preparations	Antiinfectives for local oral treat. Other agents for				
	Antiacids					
•••••	•••••					

Table 11.1.10.2 Concomitant medication characteristics started at baseline.

	Total (N=XX)				
	N	%			
No of systems (ATC1)					
0					
1					
2					
3					
> 3					
No of indications (ATC2)					
0					
1					
2					
3					
> 3					
No of agents (ATC4)					
0					

1

2

Table 11.1.10.3 Concomitant therapy started at baseline. Summary of number, indications and systems involved.

Concomitant medication (ATC1/ATC2/ATC4)	N	Median	Min	Max
Number of systems involved (ATC1)				
Number of indications involved (ATC2)				
Number of agents involved (ATC4)				

11.2. Efficacy

11.2.1. Response

Table 11.2.1 1 Patients evaluable for efficacy.

Evoluable	Total (N	=XX)
Evaluable	N	%
Yes		
No		
Total		

Table 11.2.1.2 Listing of patients excluded from the efficacy analysis.

Patient ID	Reason			
Table 11.2.1.3 Overall response rate.				
Response	N	%		
First stage				
CR+PR				
Total CR+PR				

Table 11.2.1.4 Best response in all evaluable patients.

Response	N	%
Complete Response (CR)		
Partial Response (PR)		
Stable Disease (SD)		
Progression Disease (PD)*		
Treatment Failure		

Programming Notes: Percentage is based on the total of patient evaluable for efficacy.

(*) Patients with early PD will also be included in this category (provided that they receive at least two infusions of Zalypsis®)

Table 11.2.1.5 Best response in all treated patients.

Response N %

Complete Response (CR)

Partial Response (PR)

Stable Disease (SD)

Progression Disease (PD)*

Treatment failure

Not Evaluable (NE)

Programming Notes: Percentage is based on total patient of patients treated

(*) Patients with early PD will also be included in this category (provided that they receive at least two infusions of Zalypsis®)

Table 11.2.1.6 Characteristics of responders

Patient characteristics*	Outcome prior treatment**	PM00104 treatment***

(*)Patient ID, Sex/Age/PS and Histology. (**)No. prior CT lines, last prior treatment, cycles received and best response. *** TTP, Cycles with PM104, PFS, OS.

11.2.2. Time-to-event variables

Table 11.2.2.1 Duration of response.

Summary*

N=XX

Events X (XX.X%)

Censored X (XX.X%)

Median XX 95% CI (XX.X-X.X)

(*) Responder patients by RECIST v1.1, i.e, CR and PR.

Table 11.2.2.2 Progression-free survival (Kaplan-Meier estimates in all evaluable patients).

Summary

N=XX

Events X (XX.X%)

Censored X (XX.X%)

Median XX 95% CI (X.X-X.X)

PFS rate at 3 months XX.X% 95% CI (XX.X%-XX.X%)

PFS rate at 6 months XX.X% 95% CI (XX.X%-XX.X%)

Table 11.2.2.3 Overall survival. (Kaplan-Meier estimates in all evaluable patients).

Summary

N=XX

Events X (XX.X%)

Censored X (XX.X%)

Median X.X 95% CI (XX.X-X.X)

OS rate at 12 months XX.X% 95% CI (XX.X%-XX.X%)

Table 11.2.2.4 Progression-free survival (Kaplan-Meier estimates in all treated patients).

Summary

N=XX

Events X (XX.X%)

Censored X (XX.X%)

Median XX 95% CI (X.X-X.X)

PFS rate at 3 months XX.X% 95% CI (XX.X%-XX.X%)

PFS rate at 6 months XX.X% 95% CI (XX.X%-XX.X%)

Table 11.2.2.5 Overall survival. (Kaplan-Meier estimates in all treated patients).

Summary

N=XX

Events X (XX.X%)

Censored X (XX.X%)

Median X.X 95% CI (XX.X-X.X)

OS rate at 12 months XX.X% 95% CI (XX.X%-XX.X%)

Table 11.2.2.6 Follow-up period.

Parameter	Median	95% CI Lower bound	95% CI Upper bound
PFS			
OS			

12. Appendix III. Safety evaluation

12.1. Extent of exposure

12.1.1. Treatment administration

Table 12.1.1.1 Cycles administered.

Cycles per patient: n (%)	N	0/0
1		
2		
3		

Table 12.1.1.2 Summary of cycles administered.

N	: 	Median	Min	Max	

Table 12.1.1.3 Dose intensity.

	N	Median	Min	Max
Cumulative dose (mg/m²)				
Dose intensity (mg/m² wk)				
Relative dose intensity (%)				

12.1.2. Dose administration delays

Note: Dose delays refer to delays in the administration of the first infusion of one cycle (Day 1 infusion).

Table 12.1.2.1 Dose delay

	N	%
Number of patients treated		
Number of patients susceptible of delay*		
Number of cycles administered		
Number of cycles susceptible of delay*		
Patients** with		
No delays		
1 cycle delayed		
2 cycles delayed		
≥ 3 cycles delayed		
Number of cycles with dose delay***		

Programming Notes: Percentage is based on number of cycle susceptible to be delayed.

- (*) Patients who receive only one cycle of Zalypsis[®].
- (**) Denominator: Number of patients susceptible of delay = (Total number of patients* Number of patients with first cycle only)
- (***) Denominator: Number of cycles susceptible of delay = (Number of cycles administrated Total number of first cycles)

Table 12.1.2.2 Dose delay according to their relation to study drug.

	Treatment related***		Non – Treatm	ent related
	N	%	N	%
Patients* with				
No delays				
1 cycle delayed				
2 cycles delayed				
≥ 3 cycles delayed				
Number of cycles with dosing delay *				

Programming Notes:

- (*) Patients who receive only one infusion of Zalypsis® and have treatment discontinuation within the first cycle due to any cause except for drug related AE are not susceptible of delay.
- (**) Denominator = Number of cycles susceptible to be delayed.
- (***) Hematological reason / Non-hematological reason.

Table 12.1.2.3 Length of dose delay.

	Treatmen	Treatment related**		atment related	Tota	al
	N	%	N	%	N	%
Length of delay*						
No delay						
≤ 7 days						
8 – 14 days						
> 14 days						

Programming Notes:

(*) Denominator = Number of cycles susceptible to be delayed.

(**) Hematological reason / Non-hematological reason.

Table 12.1.2.4 Dose delay and reason by cycle.

_	Су	cle 2	Cyc	cle 3	• •		To	tal
_	N	%	N	%	N	%	N	%

Number of delays

No delay

Treatment related*

Hematological reason

Non-hematological reasor

Non-treatment related*

Programming Notes: (*) Denominator = Number of cycles susceptible to be delayed.

Table 12.1.2.5 Listing of patient with dose delay.

Patient ID.	Reason for dose delay	Dose Delay Spec	Delayed Cycle	Delayed cycle start date	Previous cycle	Previous cycle start date	Dose Delay calculated. (days)
----------------	--------------------------------	-----------------------	------------------	-----------------------------------	----------------	------------------------------------	-------------------------------------

Table 12.1.2.6 Listing of patients with dose interruption and/or re-administration

Patient ID.	Cycle	Reason	Date	Intended dose	Total dose	Total volume

12.1.3. Skipped doses

Note: Infusions not administered on Days 8 and/or 15 of the cycle are considered skipped doses.

Table 12.1.3.1 Skipped doses.

at least one skipped dose

		N	0/0				
Number of patients treated wit	h at least 2 infusions						
Number of patients susceptible to have a omission							
Number of patients with any skipped dose*							
Number of patients with any skipped dose (drug related)							
Number of cycles administered	d						
Number of cycles with at least	one skipped dose (drug						
related)							
Day 8							
Day 15							
Day 8 +15							
Number of cycles with	Treatment related**	Non-	treatment related				

% (of all cycles)

% (of all cycles)

Day 8 Day 15 Day 8 +15

(**) Hematological reason / Non-hematological reason.

Table 12.1.3.2 Listing of patients with skipped doses.

Patient ID.	Cycle/infusion (skipped dose)	Reason (drug related/other)	Comments

12.1.4. Dose reduction

Note: All dose reductions will be considered and described, specifying the reason for reduction (hematological toxicity, non-hematological toxicity or other causes not related to study drug).

Table 12.1.4.1 Dose reduction.

N	%
	N

Programming Notes: Percentage is based on number of cycle susceptible to be reduced.

- (*) Patients who receive only one infusion of Zalypsis[®] and have treatment discontinuation within the first cycle due to any cause except for drug related AE are not susceptible of delay.
- (**) Denominator = Number of patients susceptible of reduction = (Total number of patients Number of patients with first cycle only)
- (***) Denominator = Number of cycles susceptible of reduction = (Number of cycles administered Total number of first cycles)

Table 12.1.4.2 Dose reduction according to their relation to study drug.

	Treatment rela	Non – Treatment related			
	N	%	N	%	
Patients* with					
No dose reductions					
1 dose reduction					
2 dose reductions					
\geq 3 dose reductions					

^(*) Patients who receive only one infusion of Zalypsis® and have treatment discontinuation within the first cycle due to any cause except for drug related AE are not susceptible of dose omission

Number of cycles with dose reduction*

Programming Notes: (*) Denominator = Number of patients/cycles susceptible to have had a dose reduced. (**) Hematological reason/Non-hematological reason.

Table 12.1.4.3 Dose reduction and reason by cycle.

	Cycle 2		Cycle	e 3		Total		
	N	%	N	%	N	%	N	%
Number of patients								
Number of reductions								
No reductions								
Treatment-related*								
Hematological reason								
Non-hematological reasc								
Non-Treatment related*								

Programming Notes. (*) Denominator = Number of patients susceptible to have had a dose reduced (who have received more than one cycle).

Table 12.1.4.4 Patients with dose reduction.

dose reduction Reduction Previous	Dose reduction Calculated (%)
-----------------------------------	----------------------------------

Table 12.1.4.5 Patients with dose delay and reduction.

Patient ID. Cycle	Reason	Comments	Dose delay (days)	(%) Reduction

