7.4.2. Cycle delays, skipped doses and dose modifications

Patients who receive only one infusion of Zalypsis[®] and have treatment discontinuation within the first cycle due to any reason different from drug related adverse event (eg: disease progression, patient's refusal), will not be considered for the calculations of the number of dose administration delays, doses skipped or dose reductions.

Dose delay is defined by a delay in the administration of the first infusion of one cycle (Day 1 infusion). Infusions not administered on Days 8 and/or 15 of the cycle are considered skipped doses and are analyzed separately.

The item "Dose delayed: No/Yes" in the case report form (CRF) will be used to calculate the delay. For doses considered as delayed by the investigator, the delay will be calculated as:

Administration delay (in days) will be equal to the date of start of the actual cycle minus the date of start of previous cycle minus 28 days (planed cycle duration, in days).

A second analysis taking into account the drug administration dates rather than the item "dose delay" completed by the investigator will be performed in order to know the calculated delay in days.

The first cycle is excluded from all calculation of cycle delay (and the denominator used for calculations will be equal to the number of cycles susceptible to be delayed).

The distribution of delays will be studied by means of counts and percentages (the denominator used for calculations will be equal to the number of patients/cycles susceptible of delay). The reasons for infusion delay will be detailed, specifying how many were due to treatment and how many were not. Within delays attributable to treatment, hematological and non-hematological reasons will be outlined, and the specific reasons will be detailed (administrative reasons will be analyzed separately and additional tables will be prepared after exclusion of those delays).

Skipped dose or dose omission is defined as every infusion not administered on Day 8 and/or 15 of the cycle. The distribution of skipped doses will be studied by means of counts and percentages (the denominator used for calculations will be equal to the number of patients/cycles susceptible to have an omission) and a detailed listing of patients with skipped

dose and reason will be showed. Also reasons for dose omission will be detailed, specifying how many were due to treatment and how many were not.

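### The dose-reduction tables use the delay denominators, with Cycle 1 removed, contrary to SAP 7.4.2; four per-cycle adverse-event tables carry a distinct-patient base

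*SAP*

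**What the plan says.** **Reductions, text.** SAP 7.4.2 defines a reduction as any dose change made after the first administration, to be described per cycle and per patient over the patients or cycles that could have been reduced. Two exclusions appear in that section:

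- For delay only: "The first cycle is excluded from all calculation of cycle delay".
- For delays, skipped doses and reductions alike, patients who had a single infusion and stopped within Cycle 1 for a reason other than a drug-related adverse event "will not be considered for the calculations of the number of dose administration delays, doses skipped or dose reductions".

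**Reductions, shells.** SAP 12.1.4 opens with "All dose reductions will be considered and described, specifying the reason for reduction". The notes to Table 12.1.4.1 then give:

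- patient base: "Denominator = Number of patients susceptible of reduction = (Total number of patients Number of patients with first cycle only";
- cycle base: "Denominator = Number of cycles susceptible of reduction = (Number of cycles administered Total number of first cycles";
- note (*), which restates the one-infusion rule but ends "due to any cause except for drug related AE are not susceptible of delay", so it speaks of delay in a reduction table.

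Table 12.1.4.3 begins at Cycle 2, and its base is "Number of patients susceptible to have had a dose reduced (who have received more than one cycle".

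**Adverse events.** SAP 12.2.1 gives Tables 12.2.1.4 to 12.2.1.11 one common layout. Its footnote bases percentages on the safety population and counts distinct patients. Tables 12.2.1.8 to 12.2.1.11 are titled as worst case per cycle. SAP 7.4.3 asks for the worst grade per patient and cycle, and SAP 8.1 takes cycles with missing adverse-event or laboratory data out of the denominator.

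**The concern.** A delay, as SAP 7.4.2 defines it, concerns only the Day 1 infusion of a cycle. Cycle 1 cannot be delayed, so removing it is right for delays. A reduction can happen at any infusion after the first, including Days 8 and 15 of Cycle 1. Carrying the delay base over to reductions removes time at risk. It also leaves a Cycle 1 reduction either without a column or in a numerator whose denominator excludes it.

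In the adverse-event tables, a count of distinct patients over the safety population is a per-patient rate, whatever the title says.

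Tolerability is a secondary objective. Two programmers, one following the shell notes and one following the SAP text, would report different rates from the same data.

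**Working it through.** **1. Can a reduction fall in Cycle 1?** Yes. Protocol 7.2.3 applies the re-treatment criteria on Days 8 and 15 of the first cycle, and Protocol 7.2.4 bases reductions on toxicity since the last dose. It is probably uncommon: a patient who fails the criteria skips the dose, and some triggers require toxicity lasting more than 5 or 7 days.

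**2. Where do the shell bases come from?** Table 12.1.2.1 (delay) subtracts first-cycle-only patients from all patients, and first cycles from cycles administered. Table 12.1.4.1 repeats both formulas. Its minus signs are lost in the text as read; I take them as subtractions because the sign is legible in the delay table's cycle note. Table 12.1.4.3 repeats the Cycle 2 start of Table 12.1.2.4 and the patient base of Table 12.1.2.1. By contrast, the skipped-dose shell (Table 12.1.3.1), also about events within a cycle, takes percentages of all cycles.

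**3. Size for reductions.** The plan states no reduction rate, so there is no figure to reproduce. Assume P = 29 treated patients, none excluded under the one-infusion rule, and 6 cycles with a reduction, k of them in Cycle 1. Let C be the total number of cycles.

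- 7.4.2 base: 6/C
- Cycle 1 dropped from numerator and denominator: (6 − k)/(C − P)
- Cycle 1 reductions counted over the shell base: 6/(C − P)

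Two values of C are used:

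- C = 58, assuming 2 cycles per patient (29 × 2).
- C = 64, from the phase I percentages in Protocol 1.2.5.1.1 (24 patients at the same dose). Between 24 and 120 cycles, only totals of 53 and 106 reproduce both 77.4% and 62.3% of cycles (41/53 and 33/53). A total of 106 is impossible with the stated median of 2 and maximum of 5 cycles, which allow at most 13 × 2 + 11 × 5 = 81. So 53/24 = 2.21 cycles per patient, and 29 × 2.21 = 64. Protocol 1.2.5.1 states 24 cycles in total at this dose; that does not fit its own median of 2 and is not used.

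| | C = 58 | C = 64 |
|---|---|---|
| 7.4.2 base | 6/58 = 10.3% | 6/64 = 9.4% |
| Dropped, k = 0 | 6/29 = 20.7% | 6/35 = 17.1% |
| Dropped, k = 1 | 5/29 = 17.2% | 5/35 = 14.3% |
| Dropped, k = 2 | 4/29 = 13.8% | 4/35 = 11.4% |
| Dropped, k = 3 | 3/29 = 10.3% | 3/35 = 8.6% |
| Dropped, k = 4 | 2/29 = 6.9% | 2/35 = 5.7% |
| Counted over shell base, any k | 6/29 = 20.7% | 6/35 = 17.1% |

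The dropped rate equals the 7.4.2 rate when the share of reductions in Cycle 1 is P/C: 29/58 = 50.0% or 29/64 = 45.3%. Below that share the shell rate is too high; above it, too low.

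**4. Size for adverse events.** Protocol 1.2.5.1.1 reports the same events on both bases:

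| Event | Patients | Cycles | Gap (points) |
|---|---|---|---|
| Nausea | 87.5% | 77.4% | 10.1 |
| Vomiting | 83.3% | 62.3% | 21.0 |
| Fatigue | 75.0% | 62.3% | 12.7 |

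Under the shared footnote, the per-cycle tables would print the first column again.

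**The case against.** SAP 7.4.2 does not define which patients or cycles count as able to be reduced, so the shell notes might be read as supplying that definition. This fails. If every first-cycle-only patient were removed, the narrower one-infusion rule would do nothing for reductions. Patients with one infusion who stop for a drug-related adverse event, whom 7.4.2 keeps, would be lost. Notes (*) and (**) of the same table would also disagree.

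Several limits do stand:

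- The row labels of Table 12.1.4.1 are lost in the text, so which rows carry which note cannot be seen.
- Table 12.1.4.2 does not repeat the subtraction, but it could inherit the definition from the table above it, so it is weak support for either reading.
- If Cycle 1 reductions are uncommon, the relevant rows are those with small k, where the shell rate is too high. Counting Cycle 1 reductions over a base without Cycle 1 is a reading few programmers would choose.
- The 64-cycle figure is inferred from a phase I population with mixed solid tumors.
- In the adverse-event tables the titles, SAP 7.4.3 and SAP 8.1 all point to a cycle base, and the note introducing the shells provides for footnotes to each table. A careful programmer may notice the conflict, but the footnote supplied for these tables is still the wrong one.
- Table 12.2.1.1 and Listings 12.1.4.4 and 12.2.1.15 would still capture a Cycle 1 reduction associated with an adverse event.

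**Conclusion.** The point holds and is minor. The notes to Tables 12.1.4.1 and 12.1.4.3 conflict with SAP 7.4.2, and the shared footnote to Tables 12.2.1.8 to 12.2.1.11 conflicts with their titles and with SAP 7.4.3 and 8.1. In the worked example the shell notes can double the reduction rate at 58 cycles (10.3% to 20.7%) or lower it by about a third when four of the six reductions fall in Cycle 1 (to 6.9%). The direction depends on the share of reductions in Cycle 1, which the documents do not give, and the difference is nil if no reductions occur. The adverse-event gap of 10 to 21 points assumes the footnote is followed literally and that phase I frequencies carry over. The response rate and the two-stage rule are untouched.

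**What to change.** In Tables 12.1.4.1 to 12.1.4.3, use the SAP 7.4.2 set throughout: all treated patients and all their cycles including Cycle 1, except one-infusion patients who stopped in Cycle 1 for a reason other than a drug-related adverse event. Specifically:

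- delete the first-cycle subtractions in notes (**) and (***) of Table 12.1.4.1;
- change delay to reduction in note (*);
- state the same base explicitly in Table 12.1.4.2;
- in Table 12.1.4.3, remove the restriction to patients with more than one cycle and add a Cycle 1 column, with the susceptible patients treated in each cycle as that column's base.

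For Tables 12.2.1.8 to 12.2.1.11, replace the shared footnote with cycles with the event divided by cycles with non-missing data, in line with SAP 8.1.

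The cost is a few programming-note edits and one added column. No new data are needed, and no dosing rule changes.
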